### **16.8. SUBGROUP ANALYSIS**

No subgroup analyses are planned for the safety parameters.

### **16.9. PHARMACOKINETIC ANALYSIS**

Plasma concentrations of SEP-363856 and its metabolite SEP-363854 will be summarized descriptively at each scheduled sample collection time point.

Plasma SEP-363856 and SEP-363854 concentrations that are below the limit of quantitation (BLQ) will be treated as zero for the computation of descriptive statistics. However, if there is at least one BLQ value for a time point, the geometric mean and geometric coefficient of variation% will not be calculated for that time point. Missing concentrations will not be imputed.

Descriptive statistics (n, mean, standard deviation, CV%, geometric mean, geometric coefficient of variation% [GCV%], median, minimum, maximum) will be used to summarize plasma SEP-363856 and SEP-363854 concentration data.

A subject listing of all plasma concentration-time data for SEP-363856 and SEP-363854 will be presented for all subjects enrolled.

Document:	\\quintiles.net\enterprise\Apps\sasdata\SASa\sas\Sunovion\S 363856\BZA44200\Biostatistics\Documentation\SAP\V1\SEF	8EP- 2 361-301 SAP Final ∖	/1.0_26JUL2023
Author:		Version Number:	Final 1.0
		Version Date:	26JUL2023
Template No.:	CS_TP_BS016 Revision 5	Reference: C	S_WI_BS005

Effective Date: 01Apr2018

Sumitomo Pharma PROTOCOL SEP361-118

Statistical Analysis Plan

### **16.10.** INTERIM ANALYSIS

No interim analysis is planned.

### APPENDIX 1. **Programming Conventions for Outputs**

### **IQVIA OUTPUT CONVENTIONS**

Outputs will be presented according to the following output conventions:

### **DATES & TIMES**

Depending on data available, dates and times will take the form yyyy-mm-ddThh:mm:ss.

#### **PRESENTATION OF TREATMENT GROUPS**

For outputs, treatment groups will be represented as follows and in that order unless shown otherwise in the output templates:

Treatment Group	For Tables and Graphs	For Listings
SEP-363856 (Overall)	SEP-363856 (Overall)	SEP-363856 (Overall)

#### **PRESENTATION OF VISITS**

For all outputs, including tables and listings, visits will be represented as follows and in that order unless shown otherwise in the output templates:

Long Name (default)	Short Name
Screening	Scr
Day -2	D-2
Day-1	D-1
Day1	D1
Baseline	BL
Week 2	W2
Week 3/Follow-up/End of Study	W3
Early Termination	ET

Early termination only applies to listings. Unscheduled visits will be presented in listings, if any.

#### LISTINGS

All listings will be ordered by the following (unless otherwise indicated in the template):

Subject ID

Date/Time (where applicable)

Document:	\\quintiles.net\enterprise\Apps\sasdata\SASa\sas\Sunovion\SEP- 363856\BZA44200\Biostatistics\Documentation\SAP\V1\SEP361-301		
Author:		Version Number:	Final 1.0
		Version Date:	26JUL2023
Template No.:	CS_TP_BS016 Revision 5	Reference: 0	CS_WI_BS005

Effective Date: 01Apr2018

### APPENDIX 2. PARTIAL DATE CONVENTIONS

Imputed dates will NOT be presented in the listings.

#### **ALGORITHM FOR TREATMENT EMERGENCE OF ADVERSE EVENTS:**

The concept of "date" below should also include time information whenever time is available for both comparators.

START DATE	STOP DATE	ACTION
Known	Known	If start date < study med start date, then not TEAE
		If start date >= study med start date, then TEAE
	Partial	If start date < study med start date, then not TEAE
		If start date $\geq$ study med start date, then TEAE
	Missing	If start date < study med start date, then not TEAE
		If start date $\geq$ study med start date, then TEAE
Partial, but known	Known	Not TEAE
cannot be on or after study	Partial	Not TEAE
med start date	Missing	Not TEAE
Partial, could be on or after	Known	If stop date < study med start date, then not TEAE
study med start date		If stop date $\geq$ = study med start date, then TEAE
	Partial	Impute stop date as latest possible date (i.e. last day of month if day unknown or 31st December if day and month are unknown), then:
		If stop date < study med start date, then not TEAE
		If stop date $\geq$ study med start date, then TEAE
	Missing	Assumed TEAE
Partial, but known	Known	TEAE
components show that it is on	Partial	TEAE

Document:	\\quintiles.net\enterprise\Apps\sasdata\SASa\sas\Sunovion\\$	SEP- 2361-301 SAP Final \	/1.0. 26 11 11 2023
Author:		Version Number:	Final 1.0
		Version Date:	26JUL2023
Template No.:	CS_TP_BS016 Revision 5	Reference: 0	CS_WI_BS005

Effective Date: 01Apr2018

PROTOCOL SEP361-118

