### **11.6.5. Physical and Neurological Examination**

A full PE as well as a neurological will be performed. The PE includes an assessment of general appearance and a review of systems (dermatologic, head, eyes, ears, nose, mouth/throat/neck, thyroid, lymph nodes, respiratory, cardiovascular, gastrointestinal, extremities, musculoskeletal, neurologic, and psychiatric systems).

All PE and neurological exam findings at screening will be captured in the medical history in the CRF. Any clinically significant changes from screening, as determined by the Investigator, will be noted as AEs in the CRF.

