## 12. SAFETY REPORTING

### 12.1. Definitions

#### 12.1.1. Adverse Events

An adverse event (AE) can be any unfavorable and unintended sign (including an abnormal laboratory finding), symptom, or disease occurring after signing the informed consent form (ICF), whether or not considered related to the medicinal (investigational) product. AEs may include the onset of new illness and the exacerbation of pre-existing conditions. AEs will be collected from the time of signing the ICF to the last study visit/EOS visit.

New signs and symptoms of underlying disease, or signs and symptoms of emerging disease must be recorded as AEs.

The Investigator should attempt to establish a diagnosis of the event based on signs, symptoms, and/or other clinical information. In such cases, the diagnosis should be documented as the AE and not the individual signs/symptoms.

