## **12.3. Collection and Recording of Adverse Events**

All AEs must be recorded in the subject's study records/source documents in accordance with the Investigator's normal clinical practice. All pre-treatment events and AEs/all AEs must be recorded on the CRF.

All AEs will be followed until resolution, stabilization of the condition, the event is otherwise explained, or the subject is lost to follow-up.

Each AE is to be evaluated for duration, severity, frequency, seriousness, action taken with the study treatment, outcome, and causal relationship to the study treatment. Definitions for severity,

frequency, action taken with the study treatment, outcome, and causal relationship to the study treatment are presented below.

The severity of AE:

- **Mild** - Ordinarily transient symptoms that do not influence performance of subject's daily activities. Other treatment is not ordinarily indicated.
- **Moderate** - Marked symptoms sufficient to make the subject uncomfortable. Moderate influence on performance of subject's daily activities. Other treatment may be necessary.
- **Severe** - Symptoms cause considerable discomfort. Substantial influence on subject's daily activities. May be unable to continue the study, and other treatment may be necessary.

The frequency of AE:

- **Once** – an isolated episode.
- **Intermittent** – occurs on two or more separate occasions.
- **Continuous** – does not abate from date of onset to date of resolution.

The action taken with the study treatment:

- **Drug Interrupted** – Study drug stopped temporarily.
- **Drug Withdrawn** – Study drug stopped permanently.
- **Dose Reduced.**
- **Dose Not Changed**
- **Not Applicable**
- **Unknown**

The outcome of the AE:

- **Recovered/Resolved**
- **Recovering/Resolving**
- **Not Recovered/Not Resolved**
- **Recovered/Resolved with Sequelae**
- **Fatal**
- **Unknown**

The causal relationship of the AE to the study treatment:

- **Not related**
  - **Not related** - Improbable temporal relationship and is plausibly related to other drugs or underlying disease.
- **Related**

- **Possible** - occurred in a reasonable time after study drug administration, but could be related to concurrent drugs or underlying disease.
- **Probable** - occurred in a reasonable time after study drug administration, is unlikely to be attributable to concurrent drugs or underlying disease, and there is a plausible mechanism to implicate the study drug.

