### **16.1. ADVERSE EVENTS**

AEs will be coded using Medical Dictionary for Regulatory Activities (MedDRA) central coding dictionary, Version 22.0.

An AE can be any unfavorable and unintended sign (including an abnormal laboratory finding), symptom, or disease

Document:	ment: \\quintiles.net\enterprise\Apps\sasdata\SASa\sas\Sunovion\SEP- 363856\BZA44200\Biostatistics\Documentation\SAP\V1\SEP361-301 SAP Final V1.0_26JUL20:					
Author:		Version Number:	Final 1.0			
		Version Date:	26JUL2023			
Template No.:	CS_TP_BS016 Revision 5	Reference: C	S_WI_BS005			

Effective Date: 01Apr2018

occurring after signing the informed consent form (ICF), whether or not considered related to the medicinal (investigational) product. AEs may include the onset of new illness and the exacerbation of pre-existing conditions. AEs will be collected from the time of signing the ICF to the last study visit/EOS visit.

TEAEs are untoward medical occurrences:

- that occurred on or after the first dose of study medication,
- with a missing start date and a stop date on or after the first dose of study medication, or
- with both a missing start date and a missing stop date.

The following TEAEs will be summarized and presented by MedDRA SOC and PT for the Safety population:

- All TEAEs (including number of events and subject incidence).
- TEAEs by severity (mild, moderate, severe).
- TEAEs by relationship to the study treatment (related, or not related).
- TEAEs by dose at onset (including number of events and subject incidence)
- TEAEs leading to study medication discontinuation (including number of events and subject incidence)
- Serious TEAEs (including number of events and subject incidence)
- TEAEs leading to study discontinuation (including number of events and subject incidence)

The following conventions will be followed in summarizing TEAEs:

- For subject incidence summaries, each subject will be counted only once within each SOC and within each preferred term.
- If a subject reports more than one TEAE within a preferred term and/or a body system, the adverse event with the highest known severity within each body system and within each preferred term will be included in the summaries by severity. Any TEAE with a missing severity will be treated as "severe" and counted in the severe category.

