- For summaries by relationship to study drug, TEAEs assessed as "possible," "probable," or "definite" will be grouped as "related." If a subject reports more than one TEAE within the same treatment regimen, SOC and PT, and any are related, it will be summarized as related. Any TEAE with a missing relationship to study medication will be regarded as "related" to study medication.
- For summaries by dose at AE onset, TEAEs will be summarized by the last actual dose level the subject was on before the onset of event. If a subject reports more than one TEAE within the same dose level, SOC and PT, it will be counted only once.

Untoward medical occurrences that occur between the time of signing the ICF and first drug administration are pre-treatment events.

A listing of AEs (TEAEs and pre-treatment events), as well as a listing of Serious TEAEs, TEAEs leading to discontinuation of study medication and discontinuation from study, TEAEs of potential drug abuse and dependence (see APPENDIX 6), and a listing of treatment emergent deaths will be presented.

See APPENDIX 2 for handling of partial dates for AEs. In the case where it is not possible to determine whether an AE began before or after dosing, the AE will be classified by the worst case; i.e. treatment emergent.

Document:	ocument:         \\quintiles.net\enterprise\Apps\sasdata\SASa\sas\Sunovion\SEP-           363856\BZA44200\Biostatistics\Documentation\SAP\V1\SEP361-301         SAP Final V1.0_26JUL:					
Author:		Version Number:	Final 1.0			
		Version Date:	26JUL2023			
Template No.:	CS_TP_BS016 Revision 5	Reference: C	S_WI_BS005			

Effective Date: 01Apr2018

Presentations regarding each of the categories described in the sub-sections below, will be provided as described and specified in the templates.

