#### 16.1.1. ALL AES

TEAEs will be summarized by System Organ Class (SOC) and Preferred Term (PT) for SEP-363856 (Overall). Listings of pre-treatment events and TEAEs will also be presented for all subjects enrolled. A listing of pre-treatment events will also be presented for screen failures.

TEAEs will also be summarized by SOC, PT and dose at event onset for SEP-363856 (Overall).

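### Treatment emergence is decided by start date with no worsening clause, so a screening-onset AE that worsens or recurs on drug drops out of the TEAE outputs if it stays under its pre-dose record

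*SAP*

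**What the plan says.** SAP 16.1 and protocol 15.3.8.1 give the same three-part definition of a TEAE. The first part is an event "that occurred on or after the first dose of study medication"; the other two deal only with missing dates. SAP Appendix 2 turns this into a decision table. With a known start date the rule is "If start date < study med start date, then not TEAE", repeated for known, partial and missing stop dates. A partial start date that is known to be before dosing gives the same result. SAP 16.1 then names the class these events fall into: "Untoward medical occurrences that occur between the time of signing the ICF and first drug administration are pre-treatment events".

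On recording, protocol 12.1.1 states that "AEs may include the onset of new illness and the exacerbation of pre-existing conditions", and SAP 16.1 repeats it. Protocol 12.3 asks for a severity and a frequency for each AE. One frequency category is Intermittent, defined as an event that "occurs on two or more separate occasions"; another is Continuous, for an event that does not abate between onset and resolution.

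On outputs, SAP 16.1.2, 16.1.3 and 16.1.6 restrict the tables and listings of drug discontinuations, study discontinuations and serious events to TEAEs. SAP 16.1.7 does the same for the listing of deaths. Protocol 15.3.8.1 plans a listing of deaths, SAEs and AEs leading to discontinuation without that restriction.

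**The concern.** AE collection starts at consent, up to 49 days before dosing, in patients already taking an antipsychotic. Symptoms such as insomnia or sedation could plausibly be on record when SEP-363856 is added. If one of them becomes severe on drug, that is the kind of signal a tolerability summary exists to show, yet the table looks only at when the record began.

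The consequence is not confined to incidence. A record that began in screening and then led to drug withdrawal, became serious or ended in death on treatment would also be absent from the dedicated outputs. The incidence of TEAEs, SAEs and AEs leading to discontinuation is one of the four listed safety endpoints. The study has a single arm, so no control group would help to reveal a gap.

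The rule also sits oddly with the SAP's own caution elsewhere. When onset cannot be placed relative to dosing, "the AE will be classified by the worst case; i.e. treatment emergent". Missing severity is counted as severe and missing relationship as related. A documented worsening on drug, by contrast, has no route to TEAE status if the known start is before first dose.

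**Working it through.** The plan gives no figure to reproduce. The check is to run the Appendix 2 table on worked cases.

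**Inputs.** The Appendix 2 decision table; the study-day convention of SAP 7.1 (Day 1 is first dose, no Day 0); screening from Day -49.

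**Rule for a known start.** TEAE if the start is on or after Day 1, otherwise not TEAE. The stop date and severity play no part.

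| Case | How it is recorded | Result |
|---|---|---|
| Starts Day -20, worsens Day 6, stops Day 15 | One record, start Day -20 | Not TEAE |
| Same event | Worsening entered as a new AE, start Day 6 | TEAE |
| Starts Day -20, resolves Day -15, recurs Day 5 | Recurrence entered as a new AE, start Day 5 | TEAE |
| Intermittent, Day -20 to Day 10 | One record, start Day -20 | Not TEAE |
| Starts Day -20, stop date missing | One record | Not TEAE |
| Partial start known to be pre-dose, stop missing | One record | Not TEAE |
| Partial start that could be on or after dosing, stops Day 3 | One record | TEAE |
| Start missing, stops Day 3 | One record | TEAE |
| Start and stop both missing | One record | TEAE |

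**All known pre-dose starts.** Days -49 to -1 give 49 possible start days. Crossed with three kinds of on-treatment stop date (known, partial, missing) that is 49 × 3 = 147 combinations; none is a TEAE.

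**What decides the outcome.** The first two rows describe the same clinical event. Only the data entry differs, so the next question is which entry the documents require.

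- Protocol 12.1.1 makes an exacerbation of a pre-existing condition an AE. It does not say that worsening of an AE already open from screening starts a new record.
- Protocol 11.6.5 says "Any clinically significant changes from screening, as determined by the Investigator, will be noted as AEs in the CRF", but this covers only physical and neurological examination findings.
- Protocol 12.3 has AEs followed until resolution or stabilisation and offers Intermittent and Continuous as frequencies, so one record spanning first dose is possible. It does not instruct sites to record events that way.
- Protocol 12.3 describes a severity evaluation for each AE but no date of worsening, so a single record may not contain what a worsening clause needs.

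The documents neither require a new record nor rule one out.

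**The case against.** The strongest reply is that on-drug exacerbations are AEs in their own right. Both documents say so; protocol 12.1.1 also requires new signs and symptoms of underlying disease to be recorded, and protocol 12.2 requires clinically significant laboratory abnormalities after dosing to be recorded. An event entered on that basis has an on-drug start date, and the algorithm counts it. This stands. A reader might infer that every screening event that worsens or recurs on drug is lost from all TEAE tables; the documents do not support that. The omission depends on how the site records the event.

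A reader might also infer that the algorithm can only undercount. It cannot be read that way as a whole: partial or missing start dates can default to TEAE and bring in events whose true onset was before dosing. The downward direction applies to known pre-dose starts.

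Other outputs soften the effect. SAP 16.1.1 says "Listings of pre-treatment events and TEAEs will also be presented for all subjects enrolled", so the record is visible somewhere, and in a study of 22 the listings can be read individually. BARS, AIMS and SAS changes, laboratory shifts and ECG shifts do not depend on AE start dates. The disposition table reports reasons for early termination. These reduce the harm but do not close the gap: non-motor symptoms without a laboratory or ECG sign have no such back-up, and a pre-treatment listing is not where a reader looks for serious events on drug.

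**Conclusion.** The point holds conditionally. An AE with a known pre-dose start that worsens or recurs on drug is omitted from the TEAE tables, and from the TEAE-only discontinuation, serious-event and death outputs, whenever it is kept under its pre-dose record. Entered as a new AE, it is counted. A pre-specified safety summary should not turn on a recording convention that the documents leave unstated.

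The size cannot be derived. One subject in 22 is 1/22 = 4.5 percentage points, but that is true of any single event and says nothing about how many are affected. Comparing collection windows is no better. Screening of 49 days against 14 + 7 = 21 days gives a ratio of 2.3; against the longest post-dose span (dosing to Day 19, follow-up 9 days later, so 28 days) it is 1.75. Neither ratio measures how often an open event worsens and stays under one record.

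The conclusion assumes that no CRF completion instruction outside these documents already settles the matter. The primary PET endpoint is not affected. The change is worth making because it is cheap and concerns core safety counts.

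**What to change.** 1. **Recording rule.** State that an increase in severity, or a recurrence, on or after first dose of an AE that began before dosing is entered as a new AE record with its own start date. The pre-dose record remains a pre-treatment event, so each worsening is counted once in the event totals.
2. **Definition.** Extend the TEAE definition in SAP 16.1 and Appendix 2 to events that began before first dose and worsened in severity or recurred on or after it. Note the departure from protocol 15.3.8.1 in SAP 4.2. The recording rule is needed alongside this clause because it supplies the date that the clause relies on.
3. **If data collection is complete.** Before database lock, review every AE record with a pre-dose start that was still open at first dose, meaning a stop date on or after first dose or no stop date. Apply the rule to those that worsened or recurred.
4. **Listings.** List all SAEs, deaths and AEs leading to discontinuation regardless of TEAE status, as protocol 15.3.8.1 plans, with TEAE status shown as a flag.

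The cost is a short SAP revision, a line of CRF guidance and a small record review. The reported TEAE rate may come out slightly higher.

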### Statistical Analysis Plan

Page 41 of 58

START DATE	STOP DATE	ACTION
or after study med start date	Missing	TEAE
Missing	Known	If stop date < study med start date, then not TEAE If stop date >= study med start date, then TEAE
	Partial	Impute stop date as latest possible date (i.e. last day of month if day unknown or 31st December if day and month are unknown), then:
		If stop date < study med start date, then not TEAE
		If stop date $\geq$ study med start date, then TEAE
	Missing	Assumed TEAE

Document:	\\quintiles.net\enterprise\Apps\sasdata\SASa\sas\Sunovion\S	EP-	
	363856\BZA44200\Biostatistics\Documentation\SAP\V1\SEF	361-301 SAP Final ∖	/1.0_26JUL2023
Author:		Version Number:	Final 1.0
		Version Date:	26JUL2023
Template No.:	CS_TP_BS016 Revision 5	Reference: C	S_WI_BS005

Effective Date: 01Apr2018

### ALGORITHM FOR PRIOR / CONCOMITANT / POST-TREATMENT MEDICATIONS:

The concept of "date" below should also include time information whenever time is available for both comparators.

For the case where the medication start date is known and is equal to the end of treatment date, and the medication start time is unknown, or the case where the imputed medication start date is equal to the end of treatment date:

- If CRF question 'Started after last dose of study medication?' = No, then assign as concomitant.
- If CRF question 'Started after last dose of study medication?' = Yes, then assign as post treatment.

START DATE	STOP DATE	ACTION
Known	Known	If stop date < study med start date, assign as prior If stop date >= study med start date and start date <= end of treatment, assign as concomitant
		If stop date >= study med start date and start date > end of treatment, assign as post treatment.
Known	Partial	Impute stop date as latest possible date (i.e. last day of month if day unknown or 31st December if day and month are unknown).
		Then:
		If stop date < study med start date, assign as prior
		If stop date >= study med start date and start date <= end of treatment, assign as concomitant
		If stop date >= study med start date and start date > end of treatment, assign as post treatment
Known	Missing	If stop date is missing could never be assumed a prior medication
		If start date <= end of treatment, assign as concomitant
		If start date > end of treatment, assign as post treatment

Document:

Author:

\\quintiles.net\enterprise\Apps\sasdata\SASa\sas\Sunovion\SEP-363856\BZA44200\Biostatistics\Documentation\SAP\V1\SEP361-301 SAP Final V1.0\_26JUL2023

Version Number: Final 1.0 Version Date: 26JUL2023 Reference: CS\_WI\_BS005

Template No.: CS\_TP\_BS016 Revision 5

Effective Date: 01Apr2018

PROTOCOL SEP361-118

